HBV PCR	X					X		Any enrolled subject who is HBcAb+ will undergo monitoring of HBV PCR. Any subject with a positive HBV PCR test at any time must be discontinued from the study and receive appropriate follow-up medical care, including consideration for antiviral therapy.
Hep C antibody	X							Positive HCV antibody will be confirmed via HCV PCR.
HIV	X							
Immunogenicity		X	X	X	X	X	X	
Serum for LY3074828 concentrations (PK)		X	X	X	X	X	X	
Serum pregnancy test	X							To be performed only on women of child bearing potential.
Urine pregnancy test		X		X	X	X	X	To be performed only on women of child bearing potential.
FSH	X							FSH test is to be performed at screening for women who have had spontaneous amenorrhea for 6 to 12 months to confirm lack of childbearing potential.
hsCRP		X	X	X	X	X	X	
CCI		█					█	
		█			█		█	

Induction Dosing Period (Visits 1-7)								
Visit No.	V1	V2	V3	V4	V5	V6	V7	Comments
Week Relative to Study Drug Start	-4	0	2	4	8	12	16	All activities should be completed prior to any study dose administration unless otherwise stated below.
Day with Visit Tolerance Interval	≤28 from V2	0	14 ± 2	28 ± 3	56 ± 5	84 ± 5	112 ± 5	Visit 1 procedures may be conducted over more than 1 day as long as all tasks are completed within the allowable visit tolerance (at least 3 days should be allowed for receipt of laboratory test results).
CCI								

Maintenance Dosing Period (Visits 8-18)												
Visit No.	V8	V9	V10	V11	V12	V13	V14	V15	V16	V17	V18	Comments
Week Relative to Study Drug Start	20	24	28	32	36	40	44	48	52	56	60	All activities should be completed prior to any study dose administration unless otherwise stated below.
Day with Visit Tolerance Interval	140 ± 5	168 ± 5	196 ± 5	224 ± 5	252 ± 5	280 ± 5	308 ± 5	336 ± 5	364 ± 5	392 ± 5	420 ± 5	
Physical examination & weight				X					X			All physical examinations throughout the study should include a symptom-directed evaluation as well as examination of heart, lungs, and abdomen and visual examination of all skin areas (including genitalia and breast areas).
Concomitant medications	X	X	X	X	X	X	X	X	X	X	X	
Adverse events	X	X	X	X	X	X	X	X	X	X	X	

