## 5. Study Design

### 5.1. Overall Design

Study AMAF is a multicenter, randomized, parallel-arm, placebo-controlled trial with 4 study periods in subjects with moderate-to-severe plaque psoriasis.

[figure not shown]
**Screening Period (≤4 weeks):** Subjects will be evaluated for study eligibility ≤28 days before the baseline visit (Visit 2/Week 0). At the baseline visit (Visit 2), subjects who fulfill the eligibility criteria will be randomized to 1 of 4 induction treatment arms.

**Induction Period (16 weeks):** A double-blind, 16-week induction period is designed to establish the efficacy and safety of LY3074828 administered at Visit 2 (Week 0) and Visit 5 (Week 8). Subjects will be randomized to 1 of 4 induction treatment arms (LY3074828 30 mg SC, LY3074828 100 mg SC, LY3074828 300 mg SC, and placebo every 8 weeks [Q8W]) stratified on the basis of previous exposure to biologic therapy for treatment of psoriasis.

**Maintenance Period (88 weeks):** The maintenance period consists of 88 weeks of treatment. At the end of the induction period (Week 16), subjects will continue treatment in the maintenance period which is intended to explore 1 of 2 treatment strategies through Week 104. All placebo subjects and subjects assigned to treatment with LY3074828 who have a <90% improvement in Psoriasis Area and Severity Index (PASI) from baseline (PASI 90) at Week 16 will receive LY3074828 300 mg SC Q8W during the entire maintenance period. Subjects with ≥PASI 90 (as needed [PRN] dosing group) at Week 16 will only be dosed with LY3074828 at the baseline dose level assignment no more frequently than Q8W when disease activity level is <PASI 90, and this will continue until ≥PASI 90 is regained. See Section 7.8.2 for maintenance period rescue treatment.

Subjects who complete Week 104 (Visit 29) of Study AMAF may be eligible to receive additional LY3074828 treatment by choosing to enroll in a separate long-term extension study, pending competent authority and/or ethical review board (ERB) approvals to conduct the separate long-term extension study.

**Follow-up Period (16 weeks):** Subjects who do not enroll in the separate long-term extension study will complete the follow-up period of Study AMAF. The follow-up period will include a visit every 4 weeks for a total of 16 weeks following Visit 29 to assess subject safety and study drug efficacy. [Figure AMAF.1](#) illustrates the study design.

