### 7.8.2. Special Treatment Considerations

Subjects in the maintenance PRN dosing arm may receive blinded rescue treatment with 300 mg Q8W. Rescue treatment may occur if not regaining a PASI  $\geq 90$  after 3 consecutive doses of retreatment or if a subject is below a PASI 50 following 1 retreatment dose. A subject starting rescue treatment will remain on that regimen through the end of the study regardless of any subsequent changes in PASI score.

All biological agents carry the risk of an injection site and/or hypersensitivity general reaction. Therefore all subjects should be closely monitored for signs or symptoms that could result from such reactions. Sites should have appropriately trained medical staff and appropriate medical equipment available when subjects are receiving study drug. If a subject experiences an acute hypersensitivity reaction after an injection of study drug, he or she should receive appropriate supportive care.

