5.1. Summary of Study Design

Study AMAF is a multicenter, randomized, parallel-arm, placebo-controlled trial with 4 study periods in subjects with moderate-to-severe plaque psoriasis.

[figure not shown]
Screening Period (≤4 weeks): Subjects will be evaluated for study eligibility ≤28 days before the baseline visit (Visit 2/Week 0). At the baseline visit (Visit 2), subjects who fulfill the eligibility criteria will be randomized to 1 of 4 induction treatment arms.

Induction Period (16 weeks): A double-blind, 16-week Induction Period is designed to establish the efficacy and safety of LY3074828 administered at Visit 2 (Week 0) and Visit 5 (Week 8). Subjects will be randomized to 1 of 4 induction treatment arms (LY3074828 30 mg SC, LY3074828 100 mg SC, LY3074828 300 mg SC, and placebo every 8 weeks [Q8W]) stratified on the basis of previous exposure to biologic therapy for treatment of psoriasis.

Maintenance Period (88 weeks): The Maintenance Period consists of 88 weeks of treatment. At the end of the Induction Period (Week 16), subjects will continue treatment in the Maintenance Period which is intended to explore 1 of 2 treatment strategies through Week 104. All placebo subjects and subjects assigned to treatment with LY3074828 who have a <90% improvement in Psoriasis Area and Severity Index (PASI) from baseline (PASI 90) at Week 16 will receive LY3074828 300 mg SC Q8W during the entire Maintenance Period. Subjects with ≥PASI 90 PRN dosing group) at Week 16 will only be dosed with LY3074828 at the baseline dose level assignment no more frequently than Q8W when disease activity level is <PASI 90, and this will continue until ≥PASI 90 is regained.

Follow-up Period (16 weeks): The Follow-up Period will include a visit every 4 weeks for a total of 16 weeks following Visit 29 to assess subject safety and study drug efficacy.

[Figure 5.1](#) illustrates the study design.

^a Visits will occur every 4 weeks in the Maintenance and Follow-up Periods.
 Abbreviations: PASI = Psoriasis Area and Severity Index; PRN = as needed; Q8W = every 8 weeks.

Figure 5.1. Illustration of study design for Clinical Protocol I6T-MC-AMAF.

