Rescue Period (Efficacy and Safety)	
All PRN subjects who received at least 1 dose of rescue treatment:
 
 • For subjects who didn't qualify for rescue treatment but get the rescue dose by mistake, they will still be included in the Rescue Period analysis population. • Unless otherwise noted, efficacy, health outcomes and safety endpoints for the Rescue Period will be analyzed on this population.
All Periods Safety	
All subjects who received at least 1 dose of LY3074828 treatment
 
 • Safety analysis will be analyzed for all subjects who were exposed to at least 1 dose of LY3074828 treatment • All LY3074828-exposed subjects will combined in the All Periods safety analysis

Abbreviation: ITT = intent-to-treat; PRN = as needed.

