6.1.2. Definitions

6.1.2.1. Study Time Intervals

Induction Period

All subjects who were randomized to the study are considered as entering the Induction Period.

The start of the Induction Period is defined as the date of first injection following randomization. For subjects who were randomized but not dosed, the Induction Period starts at the randomization date.

The end of the Induction Period is defined as the date of PASI measurement at Week 16, or the early termination date if subjects discontinued from study prior to or at Week 16, or Day 117, whichever comes first.

Maintenance Period

All subjects who had Week 16 visit with PASI measurement (except the ones discontinued the study at Week 16) are considered to have entered the Maintenance Period.

The start of the Maintenance Period is defined as the same date as end of the Induction Period, which is the date of PASI measurement at Week 16.

The end of the Maintenance Period is defined as the visit date at Week 104, or the date when the subjects received rescue treatment, or the early termination date if subjects discontinued from study prior to or at Week 104, whichever comes first.

Rescue Period

All subjects in PRN groups who received at least 1 dose of rescue treatment are considered to have entered the Rescue Period, and will be included in the Rescue Period analysis population.

The start of the Rescue Period is defined as the date the patient received the first dose of rescue treatment.

The end of the Rescue Period is defined as the visit date at Week 104, or early termination date if subjects discontinued from study prior to or at Week 104, whichever comes first.

Follow-up Period

All subjects who had Visit 29 are considered to have entered the Follow-up Period, and will be included in the Follow-up Period analysis population.

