$$(First\ study\ day\ when\ response\ is\ lower\ than\ the\ specified\ level - First\ study\ day\ when\ response\ is\ greater\ than\ or\ equal\ to\ the\ specified\ level + 1) / 7$$

If a patient does not lose response by completion or early discontinuation of the Maintenance Period, the patient will be censored with the censored date defined as the earliest date between the data cutoff for an interim analysis, the study discontinuation date, Maintenance Period end date for non-rescued patients, or the rescue start date.

Time to Recapture of Response in the Maintenance Period After PRN Dosing

Time to recapture of response (for example, PASI 90 or PASI 100) in the Maintenance Period includes only those subjects who lost the specified level of response during the Maintenance Period and is defined in weeks as:

$$(First\ study\ day\ when\ response\ is\ recaptured\ at\ the\ specified\ level - First\ study\ day\ when\ response\ is\ lower\ than\ the\ specified\ level + 1) / 7$$

If a patient does not recapture response by completion or early discontinuation of the Maintenance Period, the patient will be censored with the censored date defined as the earliest date between the data cutoff for an interim analysis, the study discontinuation date, Maintenance Period end date for non-rescued patients, or the rescue start date.

Time to Recapture of Response in the Rescue Period

Time to recapture of response (PASI 50, PASI 90, or PASI 100) in the Rescue Period includes only those subjects who lost the specified level of response during the Maintenance Period and is defined in weeks as:

$$(First\ study\ day\ when\ response\ is\ recaptured\ at\ the\ specified\ level - First\ study\ day\ when\ response\ is\ lower\ than\ the\ specified\ level + 1) / 7$$

If a patient does not recapture response by completion or early discontinuation of the Rescue Period, the patient will be censored with the censored date defined as the earliest date between the data cutoff for an interim analysis, the study discontinuation date, Rescue Period end date, and the start date of the Follow-up Period.

For variables that are not collected at each postbaseline visit, data may exist at visits where the variable was not scheduled to be collected, due to early discontinuation visits. In these situations, data from the early discontinuation visit that do not correspond to the planned

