	Time to first loss of response (PASI 90, PASI 100) for PRN subjects	KM product limit curve; time to loss of response	Maintenance Period Efficacy Population	Maintenance Period

Measure	Variable	Analysis Method (Sections 6.1.3)	Population (Section 6.1.1)	Time Point
	Time to recapture of response (PASI 90, PASI 100) after first loss of response for PRN subjects	KM product limit curve; time to response recapture after first loss of response	Maintenance Period Efficacy Population	Maintenance Period
	Time to recapture of response (PASI 50, PASI 90) after loss of response for rescued subjects	KM product limit curve; time to response recapture after first loss of response	Rescue Period Efficacy Population	Rescue Period
sPGA	sPGA (0,1); sPGA (0)	Logistic regression analysis with NRI	ITT Population	All pairwise comparisons against placebo at all postbaseline visits in Induction Period
		Summary statistics with NRI	Maintenance Period Efficacy Population	All visits in Maintenance Period
		Summary statistics (As observed) or individual trajectory line plot if total number of subjects is too small	Rescue Period Efficacy Population	All visits in Rescue Period
BSA	BSA change from baseline	MMRM; mBOCF ANCOVA	ITT Population	All pairwise comparisons against placebo at all postbaseline visits in Induction Period
		MMRM	Maintenance Period Efficacy Population	All visits in Maintenance Period
PSSI	PSSI percent improvement from baseline (for subjects with scalp psoriasis involvement only); PSSI score (for all subjects)	MMRM; mBOCF ANCOVA	ITT Population	All pairwise comparisons against placebo at all postbaseline visits in Induction Period
		MMRM	Maintenance Period Efficacy Population	All visits in Maintenance Period
	PSSI score = 0 (for all subjects)	Logistic regression analysis with NRI	ITT Population	All pairwise comparisons against placebo at all postbaseline visits in Induction Period
	Summary statistics with NRI	Maintenance Period Efficacy Population	All visits in Maintenance Period	

Measure	Variable	Analysis Method (Sections 6.1.3)	Population (Section 6.1.1)	Time Point
DLQI	DLQI (0,1), DLQI (0)	Logistic regression analysis with NRI	ITT Population	All pairwise comparisons against placebo at all postbaseline visits in Induction Period
		Summary statistics with NRI	Maintenance Period Efficacy Population	All visits in Maintenance Period

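### The SAP's Rescue Period time to PASI 90 recapture is counted from first loss in the Maintenance Period, so it includes about 4-8 or 20-24 weeks before rescue began

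*SAP*

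**What the plan says.** SAP 6.1.3 has three time-to-event definitions for the PRN groups. The third is recapture during rescue. It "in the Rescue Period includes only those subjects who lost the specified level of response during the Maintenance Period", and is the day the level is recaptured, minus the first day below the level, plus 1, divided by 7. This is the same expression as for recapture after PRN dosing in the Maintenance Period; the date of the first rescue dose is not in it. Only the censoring rule differs: the Maintenance version censors at rescue start, while the rescue version runs on to the end of the Rescue Period.

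The Rescue Period has its own start in SAP 6.1.2.1: "The start of the Rescue Period is defined as the date the patient received the first dose of rescue treatment".

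SAP Table 6.3 (section 6.9) names the variable "Time to recapture of response (PASI 50, PASI 90) after loss of response for rescued subjects", gives first loss of response as the origin, and assigns it to the Rescue Period and its population.

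Protocol 7.8.2 allows rescue if PASI 90 is not regained "after 3 consecutive doses of retreatment or if a subject is below a PASI 50 following 1 retreatment dose". Under Protocol 5.1, PRN doses are given "no more frequently than Q8W when disease activity level is <PASI 90".

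**The concern.** A subject who qualifies for rescue has already lost PASI 90 and received at least one retreatment dose. In a single loss episode, that subject is in the rescue population because PASI 90 was not regained. Starting the curve at first loss adds time during which the entry rule excludes the event. How much it adds depends on which of the two triggers led to rescue.

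The resulting median would be read as speed of response to 300 mg Q8W, but it also contains the duration of failed PRN dosing. SAP 6.9.3 presents time-to-event results by PRN arm. Arms with different mixes of triggers could show different medians even if rescue worked equally fast in all of them. SAP 5.2 says the PRN results are to support the maintenance dosing strategy for Phase 3. The loss-to-rescue weeks are also used twice: once up to censoring in the Maintenance curve, and again in the rescue curve.

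**Working it through.** The plan gives no figure for this lag, so there is none to reproduce. It follows from the schedule.

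**Inputs**
- Visit spacing: "Visits will occur every 4 weeks in the Maintenance and Follow-up Periods" (SAP 5.1).
- PRN subjects are evaluated for dosing at every visit (Protocol, Schedule of Activities), so the first retreatment dose can be given at the visit where loss is seen. The last induction dose is at Week 8 and the first possible loss visit is Week 20. That is 12 weeks, so the 8-week minimum does not delay this dose.
- PRN doses are at least 8 weeks apart (Protocol 5.1).
- The row "Day with Visit Tolerance Interval" in the Schedule of Activities allows ±5 days at each maintenance visit, so a lag between two visits can move by up to 10 days either way.
- Protocol 7.8.2 does not say whether the 8-week minimum also applies between the last PRN dose and the first rescue dose. Both readings are shown.

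**Lag from first day below PASI 90 to first rescue dose**

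The first loss and first retreatment dose are at week 0. For the three-dose trigger, the doses are at weeks 0, 8 and 16.

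| Trigger | Rescue at next visit | Rescue 8 weeks after last PRN dose |
|---|---|---|
| Below PASI 50 after 1 dose | week 4 = 28 days (18-38) | week 8 = 56 days (46-66) |
| PASI 90 not regained after 3 doses | week 20 = 140 days (130-150) | week 24 = 168 days (158-178) |

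Gap between the two routes, under the same spacing reading for both: 140 − 28 = 168 − 56 = 112 days = 16 weeks.

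**Worked example.** Two subjects lose PASI 90 at Week 40 (day 280). Each regains it 8 weeks after the first rescue dose; the 8 weeks is only illustrative. Rescue is at the next visit.

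- PASI 50 route: rescue day 308, regain day 364. SAP formula: (364 − 280 + 1)/7 = 85/7 = 12.1 weeks. From rescue: (364 − 308 + 1)/7 = 57/7 = 8.1 weeks.
- Three-dose route: rescue day 420, regain day 476. SAP formula: (476 − 280 + 1)/7 = 197/7 = 28.1 weeks. From rescue: (476 − 420 + 1)/7 = 57/7 = 8.1 weeks.

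If 8-week spacing also applies before rescue, the SAP formula gives 12.1 + 4 = 16.1 and 28.1 + 4 = 32.1 weeks; the rescue clock still gives 8.1 for both.

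**Two loss episodes.** Take loss at Week 20 (day 140), regain at Week 28 (day 196), second loss at Week 40, rescue at Week 60 (day 420) and regain at Week 68 (day 476). Read literally, the first recapture gives (196 − 140 + 1)/7 = 8.1 weeks, an event (420 − 196)/7 = 32 weeks before rescue. If only a regain after rescue counts, first loss to that regain is (476 − 140 + 1)/7 = 48.1 weeks. The rescue clock gives 8.1 weeks.

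**The case against.** The best defence is that the origin is declared. Table 6.3 says the time runs from first loss, and the words in the Rescue Period may only say where the event is counted. Under that reading a Week 28 regain, as in the two-episode example, would not count as a rescue event. The exploratory objectives in SAP 4.3 ask about the ability of retreatment to regain response after loss; none asks for time from the rescue dose. Total time out of response is a coherent quantity for a PRN strategy. Table 6.3 also plans as-observed PASI summaries at all Rescue Period visits, so this curve is not the only view of response on rescue.

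Part of this stands. Time from first loss is a legitimate summary, and the plan does not hide its origin. But declaring the origin does not keep pre-rescue time out of a median reported for the Rescue Period, and the as-observed outputs do not give time from rescue to recapture.

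On size, the 16-week gap assumes the same spacing reading for both routes; mixed readings give 20 − 8 = 12 or 24 − 4 = 20 weeks. Rescue is optional and may start later. The documents give neither the number rescued nor the trigger mix by arm, so a difference between arm medians is a possibility, not a demonstrated effect.

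**Conclusion.** The concern holds for PASI 90. The variable assigned to the Rescue Period does not measure time to response on rescue treatment. The nominal excess is 4-8 weeks by the PASI 50 trigger and 20-24 weeks by the three-dose trigger. The routes differ by 16 weeks under a common spacing reading, whatever the speed of response after rescue.

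These figures assume one loss episode, retreatment at the visit where loss is seen, doses exactly 8 weeks apart and prompt rescue. They do not carry over to PASI 50 or PASI 100, whose first-loss dates can differ. SAP Table 6.1 keeps in the rescue population subjects who did not "qualify for rescue treatment but get the rescue dose by mistake"; these may have a shorter lag or none.

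The consequence is bounded. The endpoint is exploratory, and SAP 6.3.4 limits Rescue Period efficacy to description without comparisons. The primary and secondary analyses are unaffected. The definition should still be corrected, because it determines what the planned curve measures and costs almost nothing to change.

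**What to change.** In SAP 6.1.3, define Rescue Period recapture as (first study day after the first rescue dose at which the level is regained − date of first rescue dose + 1)/7, in rescued subjects who are below that level at rescue start. The condition that the regain must follow the rescue dose also settles the two-episode case. Change the Table 6.3 entry to match, and check the general recapture wording in 6.1.3 and 6.9.3 for consistency. If total time from first loss is wanted, report it as a separate summary under its own label.

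The cost is one formula, the Table 6.3 entry and that wording check. No new data are needed: the SAP already uses the first rescue dose date as the Rescue Period start (6.1.2.1) and in the rescue exposure formula (6.12.1.1).

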6.2. Adjustments for Covariates

6.2.1. Logistic Regression

The randomization is stratified by previous biologic therapy (yes/no). Unless otherwise specified, categorical efficacy variables will be analyzed using a logistic regression analysis with treatment, geographic region (US/OUS), and previous biologic therapy (yes/no) in the model. Logistic regression details are provided in Section 6.1.3.

For primary endpoint PASI 90 at Week 16, additional covariates will be added to the logistic regression as sensitivity analysis, including baseline PASI score, treatment by previous biologic use interaction, and treatment by geographic region interaction.

